### **5.2. Serious Adverse Events**

The term “Serious Adverse Event” (SAE) is defined in 21 CFR 312.32 as follows: “An adverse event or suspected adverse reaction is considered serious if, in the view of either the investigator or the sponsor, it results in any of the following outcomes: Death, a life-threatening adverse event, inpatient hospitalization or prolongation of existing hospitalization, a persistent or significant incapacity or substantial disruption of the ability to conduct normal life functions, or a congenital anomaly/birth defect. Important medical events that may not result in death, be life-threatening, or require hospitalization may be considered serious when, based upon appropriate medical judgment, they may jeopardize the patient or subject and may require medical or surgical intervention to prevent one of the outcomes listed in this definition. Examples of such medical events include allergic bronchospasm requiring intensive treatment in an emergency room or at home, blood dyscrasias or convulsions that do not result in inpatient hospitalization, or the development of drug dependency or drug abuse.”

“Life-threatening” refers to an AE that at occurrence represents an immediate risk of death to a subject. It does not include an adverse event or suspected adverse reaction that, had it occurred in a more severe form, might have caused death. Similarly, a hospital admission for an elective procedure is not considered a SAE.

### 5.3. Adverse Event Reporting to the IND Sponsor

AEs that meet SAE criteria must be reported and submitted by the clinical site on an expedited basis to the IND Sponsor, VRC/NIAID/NIH, according to Sponsor guidelines as follows:

- Results in death
- Is life threatening
- Results in persistent or significant disability/incapacity
- Requires unplanned inpatient hospitalization or prolongation of existing hospitalization
- Is a congenital anomaly/birth defect in the offspring of a study subject
- Is an important medical event that may jeopardize the subject or may require intervention to prevent one of the other outcomes listed above.

In addition, any event, regardless of severity, which in the judgment of an investigator represents a SAE, may be reported on an expedited basis.

An investigator will communicate an initial SAE report within 24 hours of site awareness of occurrence to the IND sponsor by email to the VRC Protocol Operations Office.

A written report by the investigator should be submitted to the IND Sponsor within 3 working days. In order for the IND Sponsor to comply with regulations mandating sponsor notification of specified SAEs to the FDA within 7 and/or 15 calendar days, the investigator must submit additional information as soon as it is available.

### 5.4. IND Sponsor Reporting to the FDA

The IND Sponsor is responsible for making the determination of which SAEs are “serious and unexpected suspected adverse reactions” (SUSARs) as defined in 21 CFR 312.32.

- *Suspected adverse reaction* means any adverse event for which there is a reasonable possibility that the drug caused the adverse event.
- *Unexpected Adverse Event* means an AE that is not listed in the IB or is not listed at the specificity or severity that has been observed.

All SUSARs (as determined by the IND Sponsor) will be reported to the FDA as IND Safety Reports; IND Safety Reports will also be provided to the IRB.

The IND Sponsor will also submit an IND Annual Report of the progress of the investigation to the FDA as defined in 21 CFR 312.32.

### 5.5. Reporting to the Institutional Review Board

The following information is consistent with NIH IRB Policy 801: Reporting Research Events, Version 1, effective July 1, 2019.

Reportable Event - An event that occurs during the course of human subject research that requires notification to the IRB.

For the purposes of this policy, reportable events include the following:

- Unanticipated Problems (UPs) involving risks to subjects or others,
- Non-compliance (including major protocol deviations and noncompliance that is not related to a protocol deviation),
- Deaths related or possibly related to research activities, and
- New information that might affect the willingness of subjects to enroll or continue participation in the study.

### **5.5.1. Unanticipated Problem (UP) Definition**

An unanticipated problem (UP) is defined as any incident, experience, or outcome that meets **all** of the following criteria:

- Unexpected (in terms of nature, severity, or frequency) given (a) the research procedures that are described in the protocol-related documents, such as the IRB-approved research protocol and informed consent document; and (b) the characteristics of the subject population being studied; **and**
- Related or possibly related to participation in the research (possibly related means there is a reasonable possibility that the incident, experience, or outcome may have been caused by the procedures involved in the research); **and**
- Suggests that the research places subjects or others (which may include research staff, family members or other individuals not directly participating in the research) at a greater risk of harm (including physical, psychological, economic, or social harm) related to the research than was previously known or expected.

A UP must be reported within 7 calendar days of an investigator becoming aware of the actual or suspected UP.

### **5.5.2. Non-Compliance Definition**

Non-compliance is the failure of investigator(s) to follow the applicable laws, regulations, or institutional policies governing the protection of human subjects in research, or the requirements or determinations of the IRB, whether intentional or not.

Non-compliance may be unintentional (e.g. due to lack of understanding, knowledge, or commitment), or intentional (e.g. due to deliberate choice to ignore or compromise the requirements of any applicable regulation, organizational policy, or determination of the IRB).

Non-compliance is further characterized as serious or continuing as follows:

- Serious non-compliance - Non-compliance, whether intentional or not, that results in harm or otherwise materially compromises the rights, welfare and/or safety of the subject. Non-compliance that materially affects the scientific integrity or validity of the research may be considered serious non-compliance, even if it does not result in direct harm to research subjects.
- Continuing non-compliance- A pattern of recurring non-compliance that either has resulted, or, if continued, may result in harm to subjects or otherwise materially compromise the rights, welfare and/or safety of subjects, affect the scientific integrity of

the study or validity of the results. The pattern may comprise repetition of the same non-compliant action(s), or different noncompliant events.

Any actual or suspected non-compliance by any investigator or entity associated with the protocol must be reported to the IRB by the PI/designee within 7 calendar days of any investigator or individual associated with the protocol first becoming aware.

### **5.5.3. Protocol Deviation Definition**

A protocol deviation is defined as any change, divergence, or departure from the IRB-approved research protocol and is further characterized as major and minor as follows:

- Major Deviations – Deviations from the IRB approved protocol that have, or may have the potential to, negatively impact, the rights, welfare or safety of the subject, or to substantially negatively impact the scientific integrity or validity of the study.
- Minor Deviations – Deviations that do not have the potential to negatively impact the rights, safety, or welfare of subjects or others, or the scientific integrity or validity of the study.

For the reporting purposes, failure of subjects to comply with the research protocol does not represent non-compliance unless that failure is due to an action or omission of a member of the research team, for example, the failure to give adequate instruction to the subject.

A major deviation must be reported within 7 calendar days of an investigator becoming aware of an actual or suspected deviation. Although PDs are also non-compliance, these should only be reported once as deviations. Major deviations resulting in death must be reported within 24 hours of the occurrence of the event or of any member of the study team becoming aware of the death.

Researchers are responsible for monitoring their studies throughout the year for adherence to the IRB-approved protocol. The purpose of this monitoring is to identify major deviations and to look for trends in minor deviations that may indicate a systemic issue in how the study is being conducted that could potentially negatively impact the rights, safety, or welfare of participants or the study's ability to produce scientifically valid results. A series of minor deviations pointing toward a more global issue that could affect the rights, safety or welfare of the participant or affect the validity of the study should be reported as a major deviation. In all other instances, a summary of minor deviations should be provided to the IRB at the time of continuing review.

### **5.5.4. Death**

Any death of a research subject that is possibly, probably or definitely related to the research must be reported within 24 hours of an investigator becoming aware of the death.

### **5.5.5. New Information**

New information that might affect the willingness of a subject to enroll or remain in the study should be reported within 7 calendar days of an investigator first becoming aware.

### **5.5.6. Suspension or Termination of Research Activities**

Any suspension or termination of research activities, including holds on new enrollment, placed upon the research by the study sponsor, NIH or IC leadership, or any regulatory agency must be reported within 7 calendar days of an investigator becoming aware.

### **5.5.7. Expedited Reporting to the IRB**

Death related to research must be reported within **24 hours**.

The following will be reported within **7 calendar days** of investigator awareness:

- Actual or suspected UPs;
- Actual or suspected non-compliance;
- Actual or suspected Major PDs;
- SAEs that are actual or suspected UPs;
- New information that might affect the willingness of a subject to enroll or remain in the study;

Suspension or termination of research activities, including holds on new enrollment, placed upon the research by the study sponsor, NIH or IC leadership, or any regulatory agency.

### **5.5.8. Annual Reporting to the IRB**

The following will be reported to the IRB in summary at the time of Continuing Review:

- Summary of UPs and non-compliance;
- AEs, including SAEs, that are not UPs, as a narrative summary statement indicating whether these events were within the expected range;
- Minor PDs (aggregate summary);

Any trends or events which in the opinion of the investigator should be reported

## **6. STATISTICAL CONSIDERATIONS**

### **6.1. Overview**

This is a phase I dose-escalation study in healthy adults to assess the safety and pharmacokinetics of N6LS (VRC-HIVMAB091-00-AB), a human monoclonal antibody with broad HIV-1 neutralizing activity, with or without rHuPH20. Recruitment will target about 32 healthy adults, 18 to 50 years of age, as shown in Table 1. The permitted accrual is 40 subjects in total to allow for additional enrollments in the event that an enrolled subject does not complete the minimum evaluations needed to meet the protocol criteria for the group dose safety or dose-escalation evaluation. Dose escalation rules are described in Section 4.3.

#### **6.1.1. Treatment Assignments**

The Advantage eClinical system (Emmes Corp, Rockville, MD) will be used to assign subjects to a dose group in active accrual at the time of enrollment. If an enrolled subject is discontinued from the study before he/she has received any study product, a new eligible subject may be enrolled into the same group. If a replacement is needed in the case of a subject withdrawal, the replacement subject will be assigned to the same treatment as the dropout subject in order to complete the safety dataset as planned.

## **6.2. Sample Size Considerations**

Although the study is primarily descriptive, the primary goal is to identify safety concerns associated with different N6LS dosages in group sizes ranging from 3 to 5 subjects. For a group size of 3 subjects, there is a 90% chance of observing at least 1 SAE if the true event rate is  $\geq 0.536$  and a 90% chance of observing no SAE if the true event rate is  $\leq 0.034$ . For a group size of 5 subjects, there is a 90% chance of observing at least SAE if the true rate is  $\geq 0.37$  and a 90% chance of observing no event if the true rate is  $\leq 0.02$ . The probabilities of observing 0 and 1 or more event are presented in Table 3 for a range of possible true event rates. These calculations provide a complete picture of the sensitivity of this study design to identify potential safety problems with the study agent. For example, within the group of size n=3, if the true event rate is 0.01, then there is a probability of 0.97 to observe no event and a probability of 0.03 to observe at least 1 event; while, within the group of size n=5, if the true event rate is 0.01, then there is a probability of 0.951 to observe no event and a probability of 0.05 to observe more than 1 event.

**Table 3: Event Probabilities for Different Scenarios**

True Event Rate	Group Size, N=3		Group Size, N=5	
	Probability, No Events Observed	Probability, <math>\geq 1</math> Event Observed	Probability, No Events Observed	Probability, <math>\geq 1</math> Event Observed
0.01	0.97	0.03	0.95	0.05
0.03	0.91	0.09	0.86	0.14
0.05	0.86	0.14	0.77	0.23
0.1	0.73	0.27	0.59	0.41
0.2	0.51	0.49	0.33	0.67
0.3	0.34	0.66	0.17	0.83
0.4	0.22	0.78	0.08	0.92

Table 4 displays the upper and lower 95% exact binomial confidence bounds for all possible number of observed events in a group. For a group size of 3 subjects, the upper 95% exact confidence bound on the true rate is 0.708 if no events are observed; the lower bound will be 0.292 if all subjects experience the event. Likewise, for a group size of 5 subjects, the upper 95% exact confidence bound of the true rate is 0.522 if no events are observed; the rate of the lower bound is 0.478 if all subjects experience the event.

**Table 4: 95% Confidence Intervals of the True Rate for All Possible Number of Observed Events within a Dose Group**

Group Size, N=3 95% Confidence Interval			Group Size, N=5 95% Confidence Interval		
Observed Rate	Lower Bound	Upper Bound	Observed Rate	Lower Bound	Upper Bound
0/3	0	0.708	0/5	0	0.522
1/3	0.008	0.906	1/5	0.005	0.716
2/3	0.094	0.992	2/5	0.053	0.853
3/3	0.292	1	3/5	0.147	0.947
			4/5	0.284	0.995
			5/5	0.478	1

Table 3 and Table 4 also apply to the secondary and exploratory objectives.

### 6.3. Statistical Analysis

#### 6.3.1. Analysis Variables

The analysis variables will consist of baseline, pharmacokinetics, and safety variables to support analyses of the primary and secondary objectives.

#### 6.3.2. Baseline Characteristics

Descriptive statistics will be used to summarize baseline characteristics, inclusive of demographics and safety laboratory measurements.

#### 6.3.3. Safety Analysis

The number and percentage of subjects with one or more AEs and associated exact 95% confidence intervals will be summarized by dose group. Summaries will also include the number and percentage of subjects with any solicited or unsolicited AE, overall and by dose for each event.

##### Solicited Adverse Events:

Solicited AE data will be collected after each product administration. The number and percentage of subjects experiencing each type of solicited sign or symptom will be tabulated by severity and by dose group, select pooled groups (i.e., all IV dose groups, all 5 mg/kg SC dose groups (no rHuPH20), and all rHuPH20 dose groups), and overall (all dose groups). Subjects with multiple occurrences of the same event will be counted once using the event of highest severity.

### Adverse Events:

All unsolicited AEs reported through 56-days post each product administration will be recorded and coded by Medical Dictionary for Regulatory Activities (MedDRA) system organ class (SOC) and preferred term (PT). The number and percentages of subjects with each unsolicited AE will be tabulated by severity and relationship to the study product, by dose group, select pooled groups (i.e., all IV dose groups, all 5 mg/kg SC dose groups (no rHuPH20), and all rHuPH20 dose groups), and overall (all dose groups). Subjects with multiple occurrences of the same event will be counted once using the event highest severity or strongest relationship to the study treatment.

A by-subject listing of all unsolicited AEs will provide details including severity, relationship to treatment type, seriousness, new medical condition status, onset and end date, duration, and outcome.

### Local laboratory values:

Boxplots of local laboratory values will be generated for baseline values and for values measured during the course of the study. Each boxplot will show the 1st quartile, the median, and the 3rd quartile. Outliers, or values outside the boxplot, will also be plotted. If appropriate, horizontal lines representing boundaries for abnormal values will be plotted.

#### **6.3.4. Tolerability Evaluation**

The tolerability of an investigational medicinal product represents the degree to which overt adverse effects can be tolerated by the subject [32]. Since VRC 609 will be the first trial of N6LS in healthy adults, the tolerability evaluation will include mostly descriptive summaries of the frequency of solicited AE reports with an onset in the 3 days following each N6LS administration and subject withdrawals or discontinuations based upon subject discomfort or AEs. This early assessment of tolerability to N6LS will inform the parameters to solicit or routinely assess in future studies to further characterize the tolerability profile in a larger subject cohort.

#### **6.3.5. Pharmacokinetics Analysis**

Blood samples for PK evaluations will be collected at time-points defined in the Schedule of Evaluations (Appendix I).

**Individual Subject Pharmacokinetic Analysis:** A non-compartmental PK analysis will be performed using Phoenix 7.0 (CertaraR) or a similar program on the N6LS concentration data generated from each subject. Calculated PK parameters for IV Groups 1, 3, 4, and 6 will include: area-under-the-curve (AUC), maximum concentration ( $C_{max}$ ), time to  $C_{max}$  ( $T_{max}$ ), clearance (CL), volume of distribution ( $Vd_z$ ), terminal elimination rate constant ( $\lambda_z$ ) and the terminal half-life ( $T_{1/2}$ ). For Groups 2, 5, 7 and 8, the PK parameters will include AUC,  $C_{max}$ ,  $T_{max}$ , apparent clearance (CL/F), apparent volume of distribution ( $Vd_z/F$ ),  $\lambda_z$  and  $T_{1/2}$ .  $C_{max}$  and  $T_{max}$  will be taken directly from the observed concentration-time data. The terminal slope,  $\lambda_z$ , will be determined from the log-linear portion of the curve and the  $T_{1/2}$  calculated as  $0.693/\lambda_z$ . AUC will be determined using the linear trapezoidal method through the Week 24 PK sample for single dose groups (1-4, 7 and 8) and through Week 48 for multiple dose groups (5 and 6) or through the last PK sample with a concentration above the quantitative limit. The AUC over the

first 12 weeks following the first dose ( $AUC_{0-WK12}$ ) will be determined for all dose groups. If the final sample ( $C_{last}$ ) has a measurable N6LS concentration, the remaining AUC after the final concentration ( $AUC_{last-inf}$ ) will be estimated as  $C_{last}/\lambda_z$ . Data will be summarized by dose group and overall for IV administration groups for CL, Vd and  $T_{1/2}$ . For Groups 5 and 6, potential accumulation will be assessed as the ratios of the  $AUC_{0-WK12}$  and  $C_{max}$  for the first and the third doses. The potential for non-linearity PKs among IV groups will be determined by comparing the dose-adjusted ratios for  $C_{max}$  and  $AUC_{0-WK12}$  between IV groups. Additional compartmental analysis will be performed as warranted by the data.

**Population Pharmacokinetic Analyses:** Population PK analyses will be performed on the N6LS PK data following IV and SC administration to determine compartmental PK parameters with the PK program NONMEM version 7.3 or later (ICONR). Based on prior PK studies of bNAbs, a two compartment model will be used to analyze the N6LS PK data. The population analysis will generate estimates for initial and final volumes of distribution ( $Vd_1$  and  $Vd_2$ ), inter-compartmental clearance (Q), CL and bioavailability (F). Individual subjects' empiric Bayesian PK parameter estimates will be generated using the NONMEM posthoc subroutine. Given the small subject numbers, the population PK analysis will include a limited exploratory covariate analysis to assess dosing and clinical factors as fixed effects associated with N6LS PK parameters. The three factors that will be evaluated are dose level (5 vs 20 vs 40 mg/kg) on CL  $Vd_1$ ,  $Vd_2$  and F; repeat dosing CL  $Vd_1$ ,  $Vd_2$ , and F; and EPD co-administration on SC F and absorption rate.

The longer compartmental half-life,  $T_{1/2\beta}$  will be determined from CL,  $Vd_1$ ,  $Vd_2$  and Q using standard PK equations. Final model selection will be based on changes in the objective function and graphically by goodness of fit plots. The final population PK model will be assessed using bootstrap analysis. N6LS dosing strategies and their ability to achieve and maintain target N6LS concentrations will be performed using the final population PK model and Monte Carlo simulations with at least 5000 replicates.

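### The linear trapezoidal rule in Section 6.3.5 overstates AUC on a log-linear decline, by a few percent in most IV cases; linear-up/log-down would cut most of the error at almost no cost

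*Combined protocol and SAP*

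**What the plan says.** Section 6.3.5 (Pharmacokinetics Analysis) gives the integration rule: "AUC will be determined using the linear trapezoidal method through the Week 24 PK sample for single dose groups". Week 48 is the end point for the repeat-dose groups. No separate rule is given for the declining phase. The section takes the terminal slope from the log-linear part of the curve and, where the last sample is measurable, adds a tail equal to the last concentration divided by that slope.

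Two planned comparisons use this AUC:
- Between IV groups: "The potential for non-linearity PKs among IV groups will be determined by comparing the dose-adjusted ratios for" Cmax and AUC0-WK12.
- Between first and third doses: "For Groups 5 and 6, potential accumulation will be assessed as the ratios of the" AUC0-WK12 and Cmax.

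Bioavailability is handled elsewhere. The population model in the same section estimates F and tests "EPD co-administration on SC F and absorption rate", with dose level and repeat dosing as further covariates.

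Appendix I places samples 28 days apart after Day 28. Groups 1, 3 and 4 share Schedule 1, which has no Visit 05. That visit is the 72-hour sample in Schedule 6, so its absence implies no IV sample between Day 2 and Day 7.

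**The concern.** The plan assumes exponential decline when it extrapolates and straight lines when it integrates. On a convex falling curve the second choice always errs upward, so more subjects will not average the error out.

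A common percentage error would cancel from the dose-adjusted AUC ratios. It is common only if the curve has the same shape at every dose, and that is what the non-linearity comparison is meant to examine. The preliminary means in Section 1.4.1 suggest that shapes differ. Cmax divided by the Day 28 concentration (C28D) is 101/32 = 3.2 at 5 mg/kg IV, 589/96 = 6.1 at 20 mg/kg and 1717/43 = 40 at 40 mg/kg.

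At stake are the first human clearance estimates, the dose-adjusted AUC0-WK12 ratios, and the preliminary PK that Section 6.3.6 will use to inform dose levels in later studies.

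**Working it through.** The documents print no AUC, half-life or AUC error, so there is no stated figure to reproduce.

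**Inputs from the documents.** Section 1.4.1, mean Cmax and C28D in mcg/mL: 101 and 32 (5 mg/kg IV), 589 and 96 (20 mg/kg IV), 1717 and 43 (40 mg/kg IV). SC peak at about 6 days.

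**Assumptions.**
- Terminal half-life 24-60 days; distribution half-life 1-4 days.
- IV samples at 0, 1, 4, 24 and 48 h, Days 7, 14, 21 and 28, then every 28 days to Day 168. The early IV times are assumed because the Schedule 1 header is not legible in the text.
- An alternative C28D of 214 at 40 mg/kg. It lies between 2 x 96 = 192 and 8 x 32 = 256, the values that proportional scaling from 20 and 5 mg/kg would give.

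**One 28-day gap.** On a pure exponential, linear area / true area = (x/2) coth(x/2), with x = 28 ln2 / half-life. For 30 days, x = 0.647 and the ratio is 1.035. The overstatement is 5.4%, 3.5% and 0.9% for half-lives of 24, 30 and 60 days.

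**Whole curve.** C(t) = A exp(-at) + B exp(-bt), with A + B = Cmax and B = (C28D - Cmax exp(-28a)) / (exp(-28b) - exp(-28a)).

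Example with half-lives of 30 and 2 days:
- 5 mg/kg: A = 39.9, B = 61.1. Exact AUC0-WK12 = 2380, linear rule = 2433, error +2.2%.
- 20 mg/kg: A = 405.7, B = 183.3. Exact 7964, linear rule 8241, error +3.5%.
- Dose-adjusted 20:5 ratio: exact (7964/20)/(2380/5) = 0.837; linear (8241/20)/(2433/5) = 0.847; distortion 1.2%.

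Over the full range of assumed half-lives, for AUC0-WK12:

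| IV dose (C28D) | Linear rule | Points from before Day 28 | Points from Days 28-84 | Linear-up/log-down |
|---|---|---|---|---|
| 5 mg/kg (32) | +1.3 to +2.7% | 0.6-0.9 | 0.5-2.1 | +0.3 to +0.7% |
| 20 mg/kg (96) | +2.4 to +3.9% | 1.6-2.2 | 0.4-2.0 | +0.9 to +1.5% |
| 40 mg/kg (214, assumed) | +2.9 to +4.5% | 2.1-2.9 | 0.4-1.9 | +1.0 to +1.9% |
| 40 mg/kg (43, as printed) | +5.9 to +11.6% | 4.9-10.4 | 0.2-1.3 | +1.1 to +4.4% |

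**Dose-adjusted ratios under the linear rule.** 20:5 is distorted by 0.9-1.2%. 40:5 is distorted by 1.3-1.9% with C28D 214, or 3.6-9.0% with 43.

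**Clearance.** CL uses total AUC, whose tail is not trapezoidal. Total AUC is overstated by 1.0-2.9% at 5 mg/kg IV and 1.8-4.0% at 20 mg/kg IV; CL is understated by nearly the same percentages.

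**SC, 5 mg/kg.** A one-compartment curve with its peak at 6 days gives +0.2 to +1.7% under the linear rule and -0.3 to -0.7% under linear-up/log-down.

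**Accumulation ratio.** The error is at most 0.3% on identical first- and third-dose grids. On Group 6's differing grids it is within about 1% in most scenarios and at most 3.7%.

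**The case against.** The strongest reply is that this is a software preference with no practical consequence. Taking the printed Cmax CVs (23/101 = 23% and 236/589 = 40%) as a stand-in for AUC spread, the standard error of the log 20:5 ratio with 3 subjects per group is sqrt[ln(1 + 0.23²)/3 + ln(1 + 0.40²)/3] = 0.26. Pooling Groups 3 and 6 (n = 8) gives 0.19. The distortion is about 0.01. The comparison is descriptive, with no test or threshold, and the population model assesses dose level without any trapezoid. All of this stands and sets the priority low. It does not make the linear rule the better choice, because the error has a known sign.

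Four stronger readings are tempting and are not supported:
- **That the 28-day gaps create a dose-related bias.** Their contribution is 0.2-2.1 points and does not rise with dose. The dose-related part comes from the steep fall before Day 28.
- **That IV versus SC comparisons are biased.** Section 6.3.5 plans none on trapezoidal AUC; F and the rHuPH20 effect come from the population model. Log-down would not close the route difference either: at 5 mg/kg it is about 1 point under the linear rule and about 0.6-1.4 points after the change.
- **That the error reaches 12% at the top dose.** That rests on a C28D of 43, less than half the 96 printed for 20 mg/kg. Dose-normalised values are 6.4, 4.8 and 1.1 at 5, 20 and 40 mg/kg. With 214 the error is close to that at 20 mg/kg.
- **That log-down eliminates the error.** Part of it remains at every dose.

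**Conclusion.** The point holds as a small, systematic error of known direction. AUC0-WK12 is overstated by roughly 1-4% at 5 and 20 mg/kg IV, and clearance is understated by about 1-4%. The 40 mg/kg figure cannot be settled until its printed C28D is verified.

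The planned non-linearity comparison is affected only where curve shape differs by dose. On the printed means that is about 1% for 20:5, and more for 40:5 if 43 is correct. If shapes were the same, the relative error would cancel on the shared Schedule 1 grid.

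The direction needs only a convex decline. The sizes depend on the assumed half-lives, the biexponential form, the assumed early IV sampling times, and preliminary means from few subjects.

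**What to change.** In Section 6.3.5, replace the linear trapezoidal rule with the linear-up/log-down trapezoidal rule for all groups, and state that it also applies to AUC0-WK12 after doses 1 and 3. Separately, check the 40 mg/kg IV Day 28 concentration in Section 1.4.1 against source.

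The cost is one phrase and one setting in the non-compartmental software, with no new samples. Across the scenarios run, the IV error falls by 40% to 88%, in most by more than half. AUCs become slightly smaller, and SC AUC may be understated by about 0.3-0.7%. Any preliminary AUC already computed with the linear rule should be recomputed, so that interim and final values are comparable.
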